Title: A Randomized, Double-Blind, Phase 2a Study to Evaluate the Tolerability, Feasibility, and Efficacy of AKST1210 in Patients on Hemodialysis with Cognitive Impairment Associated with End-Stage Renal Disease

Précis: This is a randomized, double-blind study, to be conducted at up to 5 hemodialysis (HD) centers in approximately 20 evaluable subjects randomized in a 1:1 ratio (n=10 per arm) to either the AKST1210 column (the investigational treatment) or to the control (no column), to assess the tolerability, feasibility, and efficacy of AKST1210 (a beta 2-microglobulin [b2M] apheresis column) in subjects with end-stage renal disease with cognitive impairment (ESRD-CI) undergoing HD 3 times per week.

Subjects will undergo a Screening visit followed by a 2-week Run-in period. During the Run-in period, subjects' HD flow rate will be adjusted to a maximum of 250 mL/min. Subjects that meet all inclusion criteria and none of the exclusion criteria will then be randomized to either receive HD with the AKST1210 column or control (i.e., no column). The AKST1210 column will be connected in series before (upstream of) the HD cartridge for the duration of each HD session. The control will consist of a covered surrogate object of similar size/shape as the AKST1210 column which will be set up in such a way to mimic the appearance of an in-line AKST1210 column. The subject, investigator, and outcomes assessor will be blinded as to treatment.

There will be three (3) 4-week treatment periods, and all subjects will receive 3 HD treatments per week for 12 weeks. Subjects who may occasionally require an additional HD session per week would not receive the investigational intervention on that additional day. Subjects randomized to the AKST1210 column will start with a 150 mL column (S-15) used during Weeks 1 to 4 (Treatment Period 1). Subjects who meet specific criteria will undergo escalation of the column size to a 250 mL column (S-25) during Weeks 5 to 8 (Treatment Period 2) and then to a 350 mL column (S-35) during Weeks 9 to 12 (Treatment Period 3). Subjects randomized to control (no column) will receive identical escalation evaluations to maintain the treatment assignment blind. The rules specifying the criteria for escalation, de-escalation, and discontinuation are provided in [Appendix 17.1](#).

Following Treatment Period 3, subjects should resume HD in accordance with standard of care. Subjects will return for an End of Study (EOS) Visit during Week 14.

Objectives: The primary objective is evaluation of the safety and tolerability of AKST1210 for the treatment of ESRD-CI in subjects receiving HD.

The secondary objectives are to evaluate the feasibility of conducting expanded studies of AKST1210 in subjects with ESRD-CI who are undergoing HD 3 times per week as well as the efficacy of the column.

The exploratory objectives include serial compositional analysis of plasma to identify specific biomarkers possibly associated with cognitive function and/or indicators of disease progression by proteomic analyses, magnitude of b2M removal, and possible relationship to changes in cognition.

Endpoints:

Primary Endpoint:

- Incidence of treatment-emergent adverse events (TEAEs) and serious adverse events (SAEs) coded by the Medical Dictionary for Regulatory Activities (MedDRA) preferred term (PT) and MedDRA System Organ Class (SOC).

Secondary Endpoints:

- Feasibility of all procedures, including blinding.
- Tolerability of each column size escalation, as measured by subject compliance with study visit schedule/completion, visit procedures, and subject retention.
- The change in IDH Rate above each subject's Historical IDH Rate for each column size.
- The incidence of IDH leading to de-escalation or discontinuation.
- The incidence of worsening anemia by column size.
- The incidence of anemia leading to de-escalation or discontinuation.
- Change from baseline in levels of b2M at Weeks 4, 8, 12 and EOS and evaluation of any differences in the magnitude of change based on column size and duration of treatment with a specific column size.
- Change in Montreal Cognitive Assessment (MoCA) from baseline to EOS.
- Change in cognitive domains as measured with the Cogstate battery (i.e., verbal learning, psychomotor function, visual attention, working memory, executive function, and verbal delayed recall).
- Change in quality of life per the Short-Form Health Survey (SF-36).
- Change in the Patient Health Questionnaire-9 (PHQ-9).
- Change in sleep quality as measured by the Pittsburgh Sleep Quality Index (PSQI).
- Change in fatigue as measured by the Fatigue Questionnaire – Functional Assessments of Chronic Illness Therapy (FACIT).
- Changes from baseline in laboratory test data, vital sign measurements, and electrocardiograms (ECGs).

Exploratory Endpoints:

- Serial compositional analysis of plasma to identify specific biomarkers associated with cognitive function and/or indicators of disease progression by proteomic analyses.
- Magnitude of b2M removal and possible relationship to changes in cognition.

Population:

Approximately 26 male and female subjects, ≥ 40 years of age on HD with ESRD-CI, will be enrolled. Assuming a drop-out rate of 20%, enrollment at

this level will yield approximately 20 evaluable subjects.

Sample Size: Twenty (20) evaluable subjects randomized in a 1:1 ratio (n=10 per arm) to either the AKST1210 column (the investigational treatment) or to control (no column).

Phase: 2a

Number of Sites: Up to 5 sites in the US.

Description of Study device:

[figure not shown]

Description of Study Control: A covered surrogate object of similar size/shape as the AKST1210 column that will be set up in a manner that mimics the appearance of an in-line column.

Study Duration: Approximately 12 months

Subject Duration: Approximately 16-20 weeks

SCHEMATIC OF STUDY DESIGN

2 INTRODUCTION

1. **What is the primary purpose of the proposed legislation?**

1. **What is the primary purpose of the proposed legislation?**

1. **What is the primary purpose of the proposed legislation?**

For more information, contact the Office of the Vice President for Research and Economic Development at [contact] or [contact].

11. **What is the primary purpose of the *Journal of Clinical Endocrinology and Metabolism*?**

© 2013 Pearson Education, Inc.

1

1. **What is the primary purpose of the proposed legislation?**

[figure not shown]
[figure not shown]
[figure not shown]
1. **What is the primary purpose of the proposed legislation?**

11. **What is the primary purpose of the *Journal of Clinical Endocrinology and Metabolism*?**

© 2019 Pearson Education, Inc.

11 of 11

11. **What is the primary purpose of the *Journal of Clinical Endocrinology and Metabolism*?**

[REDACTED]	[REDACTED]	[REDACTED]	[REDACTED]	[REDACTED]
[REDACTED]	[REDACTED]	[REDACTED]	[REDACTED]	[REDACTED]
[REDACTED]	[REDACTED]	[REDACTED]	[REDACTED]	[REDACTED]
[REDACTED]	[REDACTED]	[REDACTED]	[REDACTED]	[REDACTED]

[REDACTED]	[REDACTED]	[REDACTED]	[REDACTED]	[REDACTED]
[REDACTED]	[REDACTED]	[REDACTED]	[REDACTED]	[REDACTED]

[REDACTED]

[REDACTED]

[REDACTED]

[REDACTED]

3 OBJECTIVES AND PURPOSE

The primary objectives of this study are to assess the safety and tolerability of AKST1210 in subjects with ESRD-CI who are receiving HD. Secondarily, this study aims to assess the feasibility of device size escalation as well as the efficacy of AKST1210. Exploratory objectives include blood and plasma collection to identify specific biomarkers associated with cognitive function and/or indicators of ESRD-CI and b2M progression.

4 STUDY DESIGN AND ENDPOINTS

4.1 DESCRIPTION OF THE STUDY DESIGN

This will be a randomized, double-blind study conducted at up to 5 sites in the US. Approximately 26 male and female subjects, \geq 40 years of age on HD with ESRD-CI, will be enrolled. Assuming a drop-out rate of 20%, enrollment at this level will yield approximately 20 evaluable subjects.

During Screening (Visit 1, Day -42 through Day -14), subjects and/or their legally authorized representative (LAR) will provide informed consent, and subjects will undergo screening assessments including provision of demographics and medical history, physical examination, 12-lead ECG, laboratory testing (including pregnancy testing if applicable), as well as tests to assess cognitive function and depression. A blood sample will also be obtained and sent to the site's local laboratory to determine baseline b2M concentration.

If the Visit 1 Screening eligibility criteria are met, subjects will commence the Run-in Period (Visits 1.1-1.6, Day -14 through Day -1). During Run-in, subjects will undergo HD at a reduced flow rate; have safety assessments; complete tests to assess cognitive function, quality of life, quality of sleep, and fatigue; and have blood samples collected for b2M and plasma proteomics. All subjects will have their HD flow rate adjusted to a maximum flow rate of 250 mL/minute, thus necessitating an increase in the overall length of dialysis time to approximately 4 hours.

Subjects who continue to meet eligibility requirements will be randomized at Visit 2 (Day 1) to one of two treatment arms: AKST1210 (the investigational treatment) or control (no column). The AKST1210 column will be connected in series before (upstream of) the HD dialyzer for the duration of each HD session, and an appropriate covering of either the AKST1210 column or control will be in place for blinding purposes. All randomized subjects will continue to undergo dialysis at the adjusted, maximum flow rate of 250 mL/minute at the extended dialysis time, similar to the Run-in Period. The subject, investigator, and outcomes assessor(s) will be blinded as to treatment (i.e., double-blind study).

There will be three (3) 4-week treatment periods, and subjects will receive 3 HD treatments with AKST1210 or control per week for 12 weeks. Subjects who may occasionally require an additional HD session per week would not receive the intervention on that additional day. Subjects randomized to the AKST1210 column will receive a 150 mL column (AKST1210 S-15) during Weeks 1 to 4 (Treatment Period 1). Subjects will then be evaluated for escalation to the 250 mL column (AKST1210 S-25) during Weeks 5 to 8 (Treatment Period 2) followed by evaluation for escalation to the 350 mL column (AKST1210 S-35) for Weeks 9 to 12 (Treatment Period 3). Subjects will be evaluated for escalation, de-escalation, or discontinuation based on specific criteria as specified in [Appendix 17.1](#). Subjects will complete an EOS Visit during Week 14.

Subjects randomized to control will also receive 3 HD treatments per week for 12 weeks for blinding purposes with similar escalation, de-escalation, and discontinuation procedures (see [Appendix 17.1](#)).

During each Treatment Period, subjects will undergo tests to assess cognitive function, quality of life, quality of sleep, and fatigue, as well as collection of blood samples for b2M and plasma proteomics. AE assessments; review of concomitant medications; targeted physical examinations; monitoring of vital signs; and assessment of fluid status will occur at every treatment visit.

In the event of early termination of a subject who has been randomized and received at least 1 HD treatment, the EOS procedures will be performed unless the subject has withdrawn consent.

The overall duration of the study/recruitment period is approximately 12 months from study initiation (i.e., following consent of first subject) to study completion (i.e., last subject, last visit). Subject participation is expected to be approximately 16 to 20 weeks, unless prematurely discontinued.

4.2 STUDY ENDPOINTS

4.2.1 PRIMARY ENDPOINT

- Incidence of TEAEs and SAEs coded by MedDRA PT and MedDRA SOC.

4.2.2 SECONDARY ENDPOINTS

- Feasibility of all procedures, including blinding.
- Tolerability of each column size escalation, as measured by subject compliance with study visit schedule/completion, visit procedures, and subject retention.
- The change in IDH Rate above each subject's Historical IDH Rate for each column size.
- The incidence of IDH leading to de-escalation or discontinuation.
- The incidence of worsening anemia by column size.
- The incidence of anemia leading to de-escalation or discontinuation.
- Change from baseline in levels of b2M at Weeks 4, 8, 12 and EOS and evaluation of any differences in the magnitude of change based on column size and duration of treatment with a specific column size.
- Change in MoCA from baseline to EOS ([Nasreddine 2005](#)).
- Change in cognitive domains as measured with the Cogstate battery (i.e., verbal learning, psychomotor function, visual attention, working memory, executive function, and verbal delayed recall).
- Change in quality of life per the SF-36 ([Laucis 2015](#)).
- Change in sleep quality as measured by the PSQI ([Buysse 1989](#)).
- Change in fatigue as measured by the FACIT ([Webster 2003](#)).
- Changes from baseline in laboratory test data, vital sign measurements, and ECGs.

4.2.3 EXPLORATORY ENDPOINTS

- Serial compositional analysis of plasma to identify specific biomarkers associated with cognitive function and/or indicators of disease progression by proteomic analyses.
- Magnitude of b2M removal and possible relationship to changes in cognition.

5 STUDY ENROLLMENT AND WITHDRAWAL

5.1 INCLUSION CRITERIA

In order to be eligible for inclusion, all subjects must meet the following criteria:

1. Male and female subjects, ≥ 40 years of age.
2. b2M level > 20 mg/L.
3. On chronic HD due to ESRD for ≥ 12 months.
4. HD performed using standard HF dialyzers (medium cut-off dialyzers are not acceptable).
5. Score on the MoCA ≥ 16 and ≤ 23 .
6. Life expectancy > 6 months (as determined by the investigator).
7. Body mass index (BMI) ≥ 20 and ≤ 36 .
8. If on medications for cognition (e.g., rivastigmine, galantamine, donepezil, memantine), must be on stable regimen for at least 8 weeks prior to Screening and remain on stable dose for the duration of the study.
9. If on antidepressant medications, must be on stable regimen for at least 8 weeks prior to Screening and remain on a stable dose for the duration of the study.
10. Must be on stable regimens (> 4 weeks) of all treatments for concomitant diseases (e.g., diabetes, hypertension, congestive heart failure).
11. The subject must be able to follow the study protocol, receive the treatment in the established timeframe, and continue during the follow-up interval.
12. The subject must have sufficient visual and auditory acuity to reliably complete all study assessments.
13. Provided a signed and dated informed consent form.

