10.4.3 ANALYSIS OF THE SECONDARY EFFICACY ENDPOINTS

The study is not powered to detect significant changes in cognition, function, etc.; however, using available data from analysis of the secondary efficacy endpoints, including changes in scores from baseline, descriptive summaries will be developed. Of particular interest will be the within-subject changes from baseline and their distribution around a null value of zero and a comparison between groups to evaluate any trends in differences between subjects randomized to active vs. control.

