4.3 Sample Size Justification

Approximately 26 male and female subjects, ≥ 40 years of age on HD with ESRD-CI, will be enrolled. Assuming a drop-out rate of 20%, enrollment at this level will yield approximately 20 evaluable subjects. Subjects will be randomized in a 1:1 ratio consisting of 1 treatment arm (AKST1210) and 1 non-active, control arm; n=10 per group. The sample

size was chosen based on clinical considerations of an exploratory study designed to test safety and tolerability ([Thabane et al., 2010](#)).

The study is not statistically powered to detect differences in measures of clinical efficacy or biomarker endpoints. In addition, the proposed sample size may be sufficient to identify trends in efficacy endpoints that will be used to determine the appropriate sample size for subsequent studies.

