5.1 General Considerations

This section presents the statistical approaches that are anticipated for the analysis of the study data. These approaches may at times require modifications due to unanticipated features of the data. Deviations from analyses summarized in this document will be noted in the CSR.

All statistical analyses will be performed using SAS® Version 9.4 or higher, unless otherwise noted. Data will be summarized using descriptive statistics, unless otherwise noted. Number of subjects (n) with non-missing values mean, median, standard deviation, minimum, and maximum will be summarized for continuous (quantitative) variables. Categorical (qualitative) variables will be summarized using frequencies and percentages of subjects who are in a particular category or each possible value. In general, the denominator for the percentage calculation will be based upon the total number of subjects in the study population for each treatment group, unless otherwise specified. The denominator for by-visit displays will be the number of subjects in the relevant study population with non-missing data at each visit. Presentations will be by treatment group (AKST1210 and Control) and Total, unless otherwise noted.

The minimum and maximum will be reported with the same degree of precision (i.e., the same number of decimal places) as the observed data. Measures of location (mean and median) will be reported to 1 degree precision more than the observed data and measures of spread (SD) will be reported to 2 degrees of precision more than the observed data.

Percentages will be presented to 1 decimal place, unless otherwise specified. Percentages will not be displayed when the numerator for a cell is 0.

Unless otherwise indicated, all statistical tests will be conducted at 0.05 significance level using 2-tailed tests, and P values will be reported. Corresponding 95% CIs will be presented for statistical tests.

In general, all summary tables will be supported by a relevant subject data listing including all subjects who are randomized. The listings will include all data collected, and will be sorted by subject ID, and actual visit date, as applicable, unless otherwise noted. The listing will also include the column size for each of the three treatment periods as applicable.

Study day 1 is the first day of HD treatment with AKST1210 or control. Study day is the day relative to the study day 1.

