Baseline is the last non-missing value prior to the start of study hemodialysis during the run-in period V1.1, unless otherwise specified. Specifically:

- All the clinical labs, PE, and ECG will use Screening as the Baseline.
- Vital signs will use V1.1 prior to first study hemodialysis as the Baseline.
- PHQ-9 and MoCA will use the Screening Visit for Baseline.
- All the other questionnaires will use Visit 2.1 as the baseline

If values are missing at the defined baseline visit above an unscheduled value will be used, provided that the unscheduled assessment occurs prior to the start of the first hemodialysis during the Run-in period V1.1.

Change from baseline is the post-treatment value minus baseline value.

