5.7.9 Change from Baseline in MoCA

The MoCA is a 1-page, 30-point test designed as a rapid scoring instrument for mild cognitive dysfunction. The questionnaire assesses several different cognitive domains, including attention and concentration, executive functions, memory, language, visuospatial skills, conceptual thinking, calculations and orientation. Higher scores indicate better cognitive function; the total possible score is 30 and a score of 26 or more is considered normal. Derivation for the MoCA total score = sum of individual item scores, with a range from 0 to 30.

Observed MoCA sub-scores and the MoCA summary score will be summarized by treatment group and Total at baseline, and at Visit 6 EOS. Change from baseline at Visit 6 EOS will also be summarized for sub-scores and summary score. The MoCA summary score are calculated within the EDC; this score will be obtained directly from the EDC data.

Within-group comparison of MoCA summary scores between baseline and Visit 6 EOS will be performed by Wilcoxon signed-rank test and associated P-values will be reported. Additionally, if the change in the MoCA summary score is normal based on Q-Q plot, the mean change from baseline in MoCA total score will be compared between treatment groups using an ANCOVA model with treatment as the main effect and baseline MoCA summary score as the covariate.

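### The Screening MoCA both selects subjects and serves as baseline, so the within-arm MoCA test is exposed to regression to the mean, in a direction the documents do not settle

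*Protocol*

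**What the plan says.** Protocol 5.1, criterion 5, requires "Score on the MoCA ≥ 16 and ≤ 23". SAP 5.1 states: "PHQ-9 and MoCA will use the Screening Visit for Baseline". The schedule tables in Protocol 15.1 place the MoCA at Screening and at EOS only, so the score that admits a subject is the only one taken before treatment.

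SAP 5.7.9 plans two analyses of the change:

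- Within each arm: "Within-group comparison of MoCA summary scores between baseline and Visit 6 EOS will be performed by Wilcoxon signed-rank test", with the P-value reported. SAP 5.1 sets the level: "all statistical tests will be conducted at 0.05 significance level using 2-tailed tests". Protocol 10.4.3 singles out "within-subject changes from baseline and their distribution around a null value of zero", and in the same sentence a comparison between the groups.
- Between arms: a comparison "using an ANCOVA model with treatment as the main effect and baseline MoCA summary score as the covariate". It is run only "if the change in the MoCA summary score is normal based on Q-Q plot", and no alternative is named if that condition fails.

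Other measures are handled differently. b2M also has an entry threshold, checked on a local Screening sample, but its analysis baseline is a separate Run-in sample (V1.5; SAP 5.4.2 and 5.7.7). Cogstate and the remaining questionnaires take their baseline at Visit 2.1, after selection.

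**The concern.** A Screening score is a true score plus measurement error. Truncating on the observed score selects on the error as well. Near the upper limit, subjects whose score happened to be low get in and those whose score happened to be high do not; near the lower limit the reverse happens. At EOS the error is drawn afresh, so the group is expected to move back towards the mean of the population that was screened. The two ends cancel only when that mean is close to the middle of the window. Otherwise the expected change with no treatment effect is not zero, and a test against zero has the wrong null.

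MoCA is a named secondary efficacy endpoint, and efficacy trends from this study are meant to inform the size of later ones (SAP 4.3). A within-arm change that is partly a selection artefact could be read as a cognitive effect and carried forward. If the Q-Q condition fails, the exposed within-arm test is the only MoCA test that remains.

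**Working it through.** **Inputs from the documents.** Window 16 to 23 inclusive, midpoint (16 + 23)/2 = 19.5. Baseline is the Screening score; there is one post-baseline score, at EOS. Two-sided level 0.05, so 2.5% in each direction. Arm size: "1 non-active, control arm; n=10 per group".

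**The plan's own figure.** 26 enrolled with 20% drop-out gives 26 × 0.8 = 20.8, about 20 evaluable, or 10 per arm. In reverse, 20/0.8 = 25, close to 26. The stated figure reproduces, and n = 10 per arm is used below. The plan states no MoCA figure to reproduce.

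**Assumptions, because the documents give none of these.** Screened-population mean μ of 18, 19.5, 22 or 24; SD 4; test-retest reliability r from 0.75 to 0.92; normal true scores; independent errors at the two visits; no treatment effect and no retest gain.

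**Formula.** Expected null change ≈ (1 − r) × (μ − mean Screening score of those admitted).

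The mean Screening score of those admitted, by simulation, is 19.07, 19.50, 20.20 and 20.71 for the four values of μ. Hence:

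- μ = 18: 0.25 × (18 − 19.07) = −0.27 at r = 0.75; 0.08 × (−1.07) = −0.09 at r = 0.92.
- μ = 19.5: 0.
- μ = 22: 0.25 × 1.80 = +0.45; 0.08 × 1.80 = +0.14.
- μ = 24: 0.25 × 3.29 = +0.82; 0.08 × 3.29 = +0.26.

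**Simulation.** Scores were rounded to whole points and limited to 0 to 30, and kept if Screening was 16 to 23. The exact signed-rank test (zeros dropped, ties allowed) was applied to samples of 10. Rounding adds a little error variance, so simulated changes can run slightly above the formula.

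| Screened mean | Null change (points) | False improvement per arm, nominal 2.5% |
|---|---|---|
| 18 | −0.27 to −0.09 | about 1% |
| 19.5 | 0 | 1-2% |
| 22 | +0.15 to +0.46 | 3-5% |
| 24 | +0.28 to +0.84 | 4-12% |

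With ties and n = 10 the exact test is conservative: with no shift it rejects in only about 3% of samples over both directions together. This is part of why the excess stays modest until the screened mean reaches about 22 to 23.

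**Wider grid.** With SD 3 to 5 and r 0.7 to 0.9, the null change is −0.35 to −0.09 at mean 18, +0.15 to +0.60 at 22 and +0.29 to +1.08 at 24. The pattern is the same.

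**The two alternatives.** In five scenarios with means from 19.5 to 25, the ANCOVA on the Screening baseline gave a mean arm difference of −0.04 to +0.01 and a false-positive rate of 0.046 to 0.050. Selecting on Screening but using a second, later pre-treatment MoCA as baseline gave an expected null change of 0.00 in all five.

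**The case against.** The strongest case against runs as follows.

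- **Direction is unknown.** The window is cut at both ends. With a screened mean below about 19.5 the artefact is a decline, and the test becomes conservative for a claim of benefit. This stands. A reader might infer that the test is biased towards improvement. The documents do not support that as a general statement. A screened mean above 19.5 is plausible, since the upper limit of 23 lies below the score of 26 that SAP 5.7.9 treats as normal, but it remains an assumption.
- **Larger error rates can be produced, but not from these documents.** Adding a practice gain on retesting raises the rate, but that is a separate mechanism with no figure in the plan. Counting a false rise in either arm also raises it, but a rise in the control arm would argue against a device effect. Neither is relied on here.
- **The design contains much of the exposure.** There is a concurrent, randomised, blinded control selected in the same way, and Protocol 10.4.3 names the between-group comparison alongside the within-subject change. This stands: regression to the mean affects both arms alike, and the ANCOVA holds its level. A reader might infer that the randomised comparison is compromised; it is not. The weak spot is that it may not be run.
- **The efficacy analyses are described as descriptive.** SAP 5.7 says so, but SAP 4.2 lists MoCA among the endpoints for hypothesis testing, and SAP 5.7.9 reports a P-value. Lack of power is no answer either, because the issue is a false positive.

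**Conclusion.** The point holds in conditional form. The design facts are certain: one Screening MoCA selects subjects and is the baseline, and its change is tested against zero within each arm. The direction and size depend on where the screened population lies, which the documents do not say. Under SD 4 and reliability 0.75 to 0.92, the artefact runs from about −0.3 points at a screened mean of 18, through nil at 19.5, to at most about +0.84 at 24. False improvement per arm runs from about 1% to about 12%, against a nominal 2.5%. Near the midpoint it is negligible.

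This concerns one secondary endpoint in a small safety study and leaves the randomised comparison intact. It is still worth correcting, because the within-arm P-value cannot be interpreted without the missing screened mean, and because the sound analysis is the one that the plan makes conditional.

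**What to change.** In SAP 5.7.9, wording only:

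1. Delete the within-arm signed-rank P-value for MoCA. Keep the within-arm change as a descriptive summary, and note that it starts from the eligibility score and may include regression to the mean in either direction.
2. Base any MoCA inference on the baseline-adjusted between-arm difference with its 95% CI.
3. Run that comparison whatever the Q-Q plot shows, or name a rank-based between-arm fallback, such as rank ANCOVA, to be used if the normality check fails. Without this step, deleting the within-arm test could leave no MoCA test at all.

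Align SAP 4.2 with this wording. The cost is the loss of one within-arm P-value.

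A second MoCA at Visit 2.1, before dialysis and alongside Cogstate, used as the analysis baseline with Screening kept for eligibility only, would remove the selection artefact from the within-arm change. It is optional. It adds one test per subject, needs a protocol schedule amendment with IRB approval before use (Protocol 12.2), and would still leave within-arm change uncontrolled for time and retesting.
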